3.3 SAFETY ENDPOINTS

[figure not shown]
To examine the acute and long-term adverse event rates associated with PVI+PWI versus PVI alone using cryoballoon ablation in patients with symptomatic PAF, including but not limited to the following:

- Vagal nerve injury resulting in GI or esophageal dysmotility
- Heart failure
- Stroke or transient ischemic attack
- Esophageal injury or atrioesophageal fistula
- Vascular access complications (*e.g.* groin site issues, vascular injury)
- Cardiac perforation, tamponade or pericardial effusion
- Pericarditis
- Phrenic nerve injury (unresolved at discharge)
- Pulmonary vein stenosis
- Major bleeding
- Myocardial infarction
- Death

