4 INTRODUCTION AND RATIONALE

Cryoballoon ablation has emerged as a safe and effective strategy for the treatment of atrial fibrillation (AF)^{1,2}, and based on growing evidence,^{2,3,4} it recently received an initial rhythm control strategy ('first-line' therapy) indication by the Food and Drug Administration. Pulmonary vein (PV) isolation (PVI) guided typically by cryoballoon PV occlusion remains the cornerstone of cryoballoon ablation. Although single-procedure freedom from recurrent AF following such an approach has been reported to be as high as 82% at 12 months,^{5,6} the success appears to be markedly diminished in the range of 50–60% during long-term follow-up.⁷ This in part may be related to the inherent limitations of cryoballoon ablation which often yields an ostial (distal) level PVI.⁸ Along these lines, prior investigations have found wide-area antral PVI encompassing the PV component (*i.e.*, the region of the posterior wall lying between the PVs) to be superior to ostial PVI.⁹ Other more recent studies involving the cryoballoon have demonstrated marked improvements in clinical efficacy associated with concomitant PVI and posterior wall isolation (PWI) within the region of the PV component as compared to PVI alone, in patients with persistent AF.^{10,11,12,13} Though widely-practiced, this approach has not been formally investigated in patients with symptomatic paroxysmal AF (PAF). Given the mechanistic similarities between persistent and PAF, we hypothesize that similar benefits may also be observed with PVI+PWI in the patients with PAF. Yet, given the relative infrequency of breakthrough/recurrent arrhythmias in patients with PAF, to detect a significant difference, large sample sizes and extended follow-up (>24 months) are likely needed. Hence, the aim of this retrospective, observational study is to examine the clinical efficacy and safety of PVI alone versus PVI+PWI using cryoballoon ablation (Figure 1), in a large cohort of patients with symptomatic PAF beyond 36 months of follow-up.

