5 STUDY DESIGN

All consecutive patients with an age >18 years and symptomatic PAF who underwent a first-time cryoballoon ablation using either PVI alone or PVI+PWI with at least 36 months of follow-up by a single operator ([name]) between 1/2014 and 12/2018 at Mercy General Hospital, will be included in this retrospective, non-randomized study. Consistent with the current definitions,³³ all patients with persistent or long-standing persistent/permanent AF will be excluded from this analysis. Baseline patient demographics, procedural and clinical findings and outcomes will be exclusively obtained from retrospective chart reviews within the Cerner electronic medical record by the study investigator or sub-investigators listed on the protocol.

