8 DATA HANDLING

All Protected Health Information (PHI) will be confidential and each subject will be assigned a unique numerical identifier which will only be used by the members of the

research team to verify accuracy and completion of data collection. This unique numerical identifier, which will correspond to each subject's Medical Record Number (MRN), will be saved in a list called the Subject Key and will be the only link to each subject's identity. This Subject Key will be destroyed upon completion of the study. All variables will be entered into an electronic database. This electronic database will be saved separately from the Subject Key and both will be stored in a folder which is access restricted, encrypted and password protected. Only Institutional Review Board approved investigators will have access to this folder.

REFERENCES

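### Long-term harms can be under-counted: outcomes come from chart review alone, with no vital-status check or rule for unknown status, and entry requires at least 36 months of follow-up

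*Combined protocol and SAP*

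**What the plan says.** All references are to the combined protocol and SAP.

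- **Source of outcomes (Section 5, Study Design).** "outcomes will be exclusively obtained from retrospective chart reviews within the Cerner electronic medical record". No other source is named.
- **Cohort (Section 5).** First-time cryoballoon ablations "between 1/2014 and 12/2018 at Mercy General Hospital", in patients "with at least 36 months of follow-up by a single operator". The 36 months is worded as a condition of entry. Section 4 gives the same horizon as the aim: "in a large cohort of patients with symptomatic PAF beyond 36 months of follow-up".
- **Safety endpoint (Section 3.3).** "To examine the acute and long-term adverse event rates associated with PVI+PWI versus PVI alone". The list includes "Stroke or transient ischemic attack", "Esophageal injury or atrioesophageal fistula", myocardial infarction, major bleeding, heart failure and death.
- **Analysis (Section 7).** Categorical variables are to be compared by chi-square or Fisher exact test at two-sided 0.05. Kaplan-Meier analysis is named only for freedom from recurrent atrial arrhythmias.
- **Identity link (Section 8).** "This Subject Key will be destroyed upon completion of the study".

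The plan does not define follow-up or last contact. It does not say how a patient of unknown status is coded, whether the Cerner record spans other hospitals, or whether outside letters are filed in it.

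**The concern.** A long-term safety comparison needs to know, for each patient, whether the event happened and until when the patient was observed. This plan secures neither.

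First, a stroke, infarction, major bleed or death managed outside the reach of the Cerner record may leave no trace in it. With a crude proportion and no unknown-status category, the patient stays in the denominator and adds nothing to the numerator.

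Second, the entry condition selects on the future. A patient who dies or is lost before month 36 does not have 36 months of follow-up, and on a literal reading is not in the study.

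What is at stake is the reassurance the study can offer about adding posterior wall isolation. Low event rates, or a non-significant difference, could reflect what was looked for and who was kept rather than the procedure. Once the Subject Key is destroyed, the gap can no longer be repaired.

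**Working it through.** **Plan's own figure.** The only design figure is the target of about 1,000 patients (Section 6). It has no power, effect size, event rate or split by arm, so it cannot be reproduced. The point does not depend on it.

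**Inputs for the illustration.** From the documents: total of about 1,000, Fisher exact test, two-sided 0.05. Assumed: 500 per arm; true long-term serious event rates of 4% (PVI) and 7% (PVI+PWI); capture of 100%, 80% or 60%.

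**Step 1: equal capture.** Observed rate = true rate × capture. Power is by exact enumeration of Fisher's test.

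| Capture | Observed rates | Expected events | Difference | Risk ratio | Fisher power |
|---|---|---|---|---|---|
| 100% | 4.0% v 7.0% | 20 v 35 | 3.0 points | 1.75 | 50% |
| 80% | 3.2% v 5.6% | 16 v 28 | 2.4 points | 1.75 | 40% |
| 60% | 2.4% v 4.2% | 12 v 21 | 1.8 points | 1.75 | 30% |

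Capture cancels from the ratio: (7% × c)/(4% × c) = 1.75 for any c. It does not cancel from the difference: (7% − 4%) × c. P-values at the expected counts are a poor guide here, because 20 v 35 of 500 already gives Fisher P = 0.051 with nothing missed (0.089 at 80%, 0.156 at 60%).

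**Step 2: other assumed rates.** With 2% v 5% and 500 per arm, exact Fisher power is 70%, 55% and 36% at 100%, 75% and 50% capture. The direction is the same.

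**Step 3: unequal capture.** Assume true rates of 2% v 4%, a risk ratio of 2.0.

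- Capture 90% v 45%: 2% × 0.90 = 1.8% and 4% × 0.45 = 1.8%, so the ratio is 1.0.
- Capture 50% v 80%: 2% × 0.50 = 1.0% and 4% × 0.80 = 3.2%, so the ratio is 3.2.

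The bias can run either way.

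**Step 4: rare events.** For an assumed true risk of 0.2% in 500 patients, the chance of recording none is (1 − 0.002 × c)^500: 37% at full capture, 47% at 75% and 61% at 50%.

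**Step 5: the entry condition.** Suppose N eligible patients are treated and d of them die before month 36. The true 36-month mortality is d/N. Under the literal entry rule all d are removed, so the observed figure is 0/(N − d) = 0 in either arm, whatever d is. Non-fatal events in those patients, and in patients lost before month 36, go with them. Searching outside records only for the patients who remain would not bring them back.

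**The case against.** - **Many listed harms arise at or near the procedure.** Access complications, tamponade and phrenic nerve injury present at discharge should be in the treating hospital's chart. This stands, and confines the point to post-discharge events.
- **The Cerner record may cover a network or hold outside documents.** The text does not exclude this, so calling it one hospital's record goes further than the wording. Reviewing outside documents already filed there may be permitted as the plan stands. That could make capture high, but the plan neither claims this nor proposes to measure it.
- **Retained patients have at least 36 months of follow-up, so few should vanish unnoticed.** This has some force, but follow-up is undefined, and the same condition causes the selection in Step 5.
- **A reader might infer that the study will find equal risk.** The documents do not support that. Equal under-capture preserves the risk ratio, and unequal capture can exaggerate a difference as well as hide it. In the 4% v 7% example power is only about 50% with nothing missed, so limited sample size accounts for much of the chance of a non-significant result.
- **A reader might infer that deaths and fatal fistulas treated elsewhere are scored as event-free.** The plan has no coding rule, so this is only the default consequence of a crude proportion. For deaths before month 36 the literal effect is exclusion from the cohort.
- **Destroying the Subject Key is a privacy safeguard.** Agreed; only its timing matters here.

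**Conclusion.** The concern holds for post-discharge harms. The plan limits outcomes to chart review, supplies no ascertainment of vital status or outside events, has no rule for unknown status, and conditions entry on 36 months of follow-up. Each of the two mechanisms, missed events and selective entry, lowers observed absolute risk.

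Under equal capture with assumed rates of 4% v 7% and 500 per arm, the difference falls from 3.0 to 2.4 or 1.8 points and Fisher power from about 50% to 40% or 30%; the risk ratio stays at 1.75. Under unequal capture the direction of bias is unknown. The rates, the capture levels and the 1:1 split are assumptions. True capture and the scope of the Cerner record are not in the documents, so the actual size of the loss cannot be stated. The effect of the entry condition rests on reading Section 5 literally.

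The supportable conclusion is that long-term risk may be under-stated and a real difference more easily missed, not that the study must report equal safety. This should be corrected before any reassuring long-term safety statement is made.

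**What to change.** 1. For the safety analysis, include all consecutive eligible procedures from the ablation date, without the 36-month requirement.
2. Delete the restriction to chart review as the exclusive source of outcomes.
3. Before the Subject Key is destroyed, match all of these patients once to a death index or vital records.
4. For patients with gaps in contact, review outside records viewable from the chart. State what the Cerner record covers.
5. Define last contact. Analyse post-discharge safety events by time-to-event methods or person-time rates, censoring at last contact. Do not count unknown status as event-free.
6. Report by arm the proportion with confirmed vital status, and with documented contact at 3, 12 and 36 months.

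Steps 1 and 3 belong together: matching only patients who met the 36-month condition would not recover those it removed.

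The cost is an IRB amendment, a small linkage fee and some extra chart review, with no patient contact. Reported event rates may come out higher.

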6 SAMPLE SIZE

The target sample size for this study is approximately 1,000 patients.

7 STATISTICAL METHODS

Baseline patient demographics, procedural and clinical characteristics will be recorded for the entire cohort. Continuous variables will be analyzed using the two-sample *t* test or Mann-Whitney test for parametric and non-parametric variables, respectively. The χ^2 or Fisher exact test will be used for parametric or non-parametric categorical variables, respectively. For freedom from recurrent atrial arrhythmias, a Kaplan-Meier modeled analysis will be performed. For all analyses, P-values will be two-sided and a $P<0.05$ will be considered statistically significant. The analyses will be conducted with use of SPSS Version 20 (IBM SPSS Statistics, Chicago, IL).

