2 OBJECTIVE

To examine the efficacy and safety of posterior wall isolation (PWI) within the region of the PV component in conjunction with pulmonary vein (PV) isolation (PVI) versus PVI alone using cryoballoon ablation for the treatment of patients with symptomatic paroxysmal atrial fibrillation (PAF) during long-term follow-up

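### Section 7 names no analysis for the safety endpoint: adverse events get at most a generic chi-square or Fisher P value, with no risk difference or confidence interval

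*Combined protocol and SAP*

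**What the plan says.** The introduction (section 4) gives the aim as "to examine the clinical efficacy and safety of PVI alone versus PVI+PWI using cryoballoon ablation", and section 2 likewise names safety beside efficacy. Section 3.3 turns this into an endpoint, "To examine the acute and long-term adverse event rates associated with PVI+PWI versus PVI alone", followed by a list of 12 event types that is expressly not exhaustive.

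Section 7 names an analysis for one outcome: "For freedom from recurrent atrial arrhythmias, a Kaplan-Meier modeled analysis will be performed". Adverse events, complications and safety do not appear in it. The text that could reach them is general: a chi-square test or "Fisher exact test will be used for parametric or non-parametric categorical variables, respectively", together with "For all analyses, P-values will be two-sided" and a significance threshold of 0.05. No risk difference, risk ratio or confidence interval is specified for any outcome.

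On size, section 6 says only "The target sample size for this study is approximately 1,000 patients". It gives no split between the two strategies, no event rates and no power statement.

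**The concern.** A comparison of harms has to show how large an increase the data still allow. A P value does not show this; an interval does. When events are uncommon, a non-significant test is the likely result even if the risk has doubled, and the plan provides nothing that would tell a reader whether the arms are similar or the events too few. For an event with no cases in either arm there is no informative P value at all, although an interval can still be given.

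At stake is the safety half of the study's conclusion. Without a planned interval, a table of non-significant P values is easily taken as reassurance about adding posterior wall isolation.

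**Working it through.** **Inputs.** From the documents: about 1,000 patients in total (section 6), a two-sided test at 0.05 (section 7) and 12 listed event types (section 3.3). Assumed, because the documents are silent: arm sizes of 500/500, with 700/300 and 300/700 as alternatives (PVI/PVI+PWI), and event risks of 1%, 2% and 5% under PVI. The plan states no safety figure, so there is none to reproduce.

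**Power to detect a doubling of risk.** Obtained by enumerating all pairs of counts from two independent binomials and summing the probability of those with two-sided P<0.05 (uncorrected chi-square / Fisher):

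| Split | Risks | Chi-square | Fisher |
|---|---|---|---|
| 500/500 | 1% v 2% | 24% | 18% |
| 500/500 | 2% v 4% | 46% | 40% |
| 500/500 | 5% v 10% | 86% | 83% |
| 700/300 | 1% v 2% | 28% | 20% |
| 300/700 | 1% v 2% | 17% | 15% |

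From a 1% baseline, a doubling is missed between 72% (100 - 28) and 85% (100 - 15) of the time across these splits and tests.

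**What an interval adds.** The Newcombe interval combines the Wilson limits of each arm. With z = 1.96, the Wilson limits are [p + z²/2n ± z√(p(1-p)/n + z²/4n²)] / (1 + z²/n). For a difference d = p1 - p2 (PVI+PWI minus PVI):

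- lower = d - √[(p1 - l1)² + (u2 - p2)²]
- upper = d + √[(u1 - p1)² + (p2 - l2)²]

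Wilson limits in percent: 0/500 gives 0 to 0.762; 5/500 gives 0.428 to 2.319; 10/500 gives 1.090 to 3.642.

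Results in percentage points, with counts as PVI v PVI+PWI:

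- **5/500 v 5/500.** d = 0; half-width √[(2.319 - 1)² + (1 - 0.428)²] = 1.44. Interval -1.44 to +1.44, with P=1.00. From an observed 1%, a rise to about 2.4% (1 + 1.44) is not excluded.
- **5/500 v 10/500.** d = +1.00; lower 1 - √[(2 - 1.090)² + (2.319 - 1)²] = -0.60; upper 1 + √[(3.642 - 2)² + (1 - 0.428)²] = +2.74. P=0.19 (chi-square) or 0.30 (Fisher).
- **0/500 v 0/500.** Each arm's upper limit is 0.762, so the interval is -0.76 to +0.76, with no informative P. At 700/300 it is -0.55 to +1.26.
- **0/500 v 5/500.** d = +1.00; lower 1 - √[(1 - 0.428)² + 0.762²] = +0.05; upper 1 + (2.319 - 1) = +2.32. Fisher P=0.062, chi-square P=0.025.

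The last case shows that the interval and the Fisher P can fall on opposite sides of the border.

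**The case against.** The strongest reply is that a test is in fact available. Yes/no adverse events are categorical variables, and section 7 gives a rule for those and a threshold for all analyses. That stands. A reader might infer that the plan contains no safety analysis of any kind, but the text does not support so strong a statement; what is missing is a named analysis, an effect estimate and an interval.

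Second, the gap is not peculiar to safety. This is also true: section 7 plans no estimate or interval for recurrence either. It widens the omission rather than excusing it. It matters particularly for safety, because there a non-significant result is easily read as good news.

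Third, nothing says that every listed event is rare. The list runs from vascular access problems and pericarditis to death. At a 5% baseline the power for a doubling is above 80% at 500/500, so the argument is confined to the rarer events.

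Fourth, the plan announces no equivalence or non-inferiority claim, and a reader given the counts could compute the interval. A reader might infer that the sponsor intends to declare equal safety from P>=0.05; the documents say no such thing. But they do not guard against that reading, and section 7 does not promise the counts.

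Finally, crude intervals in a non-randomized cohort can suggest more assurance than the design gives. That is a fair caution and belongs beside the intervals in the report.

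**Conclusion.** The concern holds in limited form. Comparative adverse event rates are an aim and an endpoint, yet section 7 offers them at most a generic two-sided P value, with no risk difference or confidence interval. No stated figure is wrong.

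The size depends on assumed arm sizes and event rates. With 500 per arm, the test detects a doubling about one time in four or fewer from a 1% baseline, in 40% to 46% of cases from 2%, and in 83% to 86% from 5%. At 1% the conclusion is the same for the 700/300 and 300/700 splits. For the rarer events, a non-significant P therefore cannot separate no increase from too few events. This is an improvement that should be made, at little cost.

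**What to change.** Add to section 7:

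*Each adverse event recorded under section 3.3, whether or not it is listed there, will be reported separately for the acute and long-term periods as n/N per arm, where N is all treated patients in that arm included in the cohort. The unadjusted risk difference (PVI+PWI minus PVI) will be given with a 95% score-type confidence interval suited to rare events (for example Newcombe). Statements on relative safety will rest on these intervals, and P>=0.05 will not be read as evidence of equal safety.*

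The sponsor also needs to state where the acute period ends, since neither section 3.3 nor section 7 does so.

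The cost is a few sentences; the intervals need only the event counts and denominators in each arm. There are three downsides. The safety statement becomes more cautious. The interval will sometimes disagree with the Fisher P, as in 0/500 v 5/500 (+0.05 to +2.32 points, P=0.062), which is why the text must say that the interval carries the statement. And the intervals are not adjusted for multiplicity across event types, for confounding, or for the selection created by including only patients "with at least 36 months of follow-up by a single operator" (section 5). That condition may leave out early deaths, although death is a listed event. The report should state these limits beside the intervals.

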8 DATA HANDLING

All Protected Health Information (PHI) will be confidential and each subject will be assigned a unique numerical identifier which will only be used by the members of the

research team to verify accuracy and completion of data collection. This unique numerical identifier, which will correspond to each subject's Medical Record Number (MRN), will be saved in a list called the Subject Key and will be the only link to each subject's identity. This Subject Key will be destroyed upon completion of the study. All variables will be entered into an electronic database. This electronic database will be saved separately from the Subject Key and both will be stored in a folder which is access restricted, encrypted and password protected. Only Institutional Review Board approved investigators will have access to this folder.

REFERENCES

